7.3 LOST TO FOLLOW-UP

A participant will be considered lost to follow-up if he or she fails to return for scheduled visit(s) and is unable to be contacted by the study site staff.

The following actions must be taken if a participant fails to return to the clinic for a required study visit:

1. The site will attempt to contact the participant and reschedule the missed visit and counsel the participant on the importance of maintaining the assigned visit schedule and ascertain if the participant wishes to and/or should continue in the study.
2. Before a participant is deemed lost to follow-up, the investigator or designee will make every effort to regain contact with the participant (where possible, 3 telephone calls and, if necessary, a certified letter to the participant's last known mailing address or local equivalent methods). These contact attempts should be documented in the participant's medical record or study file.
3. Should the participant continue to be unreachable, he or she will be considered to have withdrawn from the study with a primary reason of lost to follow-up.

8 STUDY ASSESSMENTS AND PROCEDURES

8.1 SAFETY AND OTHER ASSESSMENTS

This study will comply with all applicable regulations on IND safety reporting requirements to the FDA in accordance with 21 CFR 312.32. This study will utilize CTCAE v5.0 for toxicity and AE reporting. All appropriate treatment areas at the clinical sites will have access to a copy of the CTCAE v5.0. Careful evaluation to determine the toxicity IFx-Hu2.0 as a monotherapy will be performed. Adverse events will be documented beginning at initiation of treatment (Day 0) as well as at the follow-up visit whether that be end of study as planned or early termination.

Subjects with treatment-related toxicity will be followed for the ongoing drug-related adverse events until resolved, return to baseline, deemed irreversible by the treating physician, the subject has been properly referred to an appropriately licensed practitioner for further evaluation and treatment, or until the subject is lost to follow up, withdrawal of study consent, removal of the subject from the trial by the treating physician, or start of a subsequent anti-cancer therapy.

8.2 ADVERSE EVENTS AND SERIOUS ADVERSE EVENTS

8.2.1 DEFINITION OF ADVERSE EVENTS (AE) (21 CFR 312.32(A))

An AE is defined as any untoward medical occurrence associated with the use of an intervention in humans, whether or not considered intervention-related (21 CFR 312.32 (a)).

An ongoing or intermittent adverse event should be recorded only once, with the highest/worst grade reported for the event. This study will utilize the Common Terminology Criteria for Adverse Events version 5 (CTCAE v5) for toxicity and adverse event reporting.

8.2.2 DEFINITION OF SERIOUS ADVERSE EVENTS (SAE) (21 CFR 312.32(A))

An adverse event (AE) or suspected adverse reaction is considered "serious" if, in the view of either the investigator or sponsor, it results in any of the following outcomes: death, a life-threatening adverse event, inpatient hospitalization or prolongation of existing hospitalization, a persistent or significant incapacity or substantial disruption of the ability to conduct normal life functions, or a congenital anomaly/birth defect in the offspring of a participant. Important medical events that may not result in death, be life-threatening, or require hospitalization may be considered serious when, based upon appropriate medical judgment, they may jeopardize the participant and may require medical or surgical intervention to prevent one of the outcomes listed in this definition. Examples of such medical events include allergic bronchospasm requiring intensive treatment in an emergency room or at home, blood dyscrasias or convulsions that do not result in inpatient hospitalization, or the development of drug dependency or drug abuse.

8.2.3 CLASSIFICATION OF AN ADVERSE EVENT

8.2.3.1 SEVERITY OF EVENT

For AEs not included in the protocol defined grading system, the following guidelines will be used to describe severity:

1. **Mild** – Events require minimal or no treatment and do not interfere with the participant's daily activities.
2. **Moderate** – Events result in a low level of inconvenience or concern with the therapeutic measures. Moderate events may cause some interference with functioning.
3. **Severe** – Events interrupt a participant's usual daily activity and may require systemic drug therapy or other treatment. Severe events are usually potentially life-threatening or incapacitating.

8.2.3.2 RELATIONSHIP TO STUDY INTERVENTION

All adverse events (AEs) must have their relationship to study intervention assessed by the investigator who examines and evaluates the participant based on temporal relationship and his/her clinical judgment. The degree of certainty about causality will be graded using the categories below. In a clinical trial, the study product must always be suspect.

1. **Definitely Related** – There is clear evidence to suggest a causal relationship, and other possible contributing factors can be ruled out. The clinical event, including an abnormal laboratory test result, occurs in a plausible time relationship to study intervention administration and cannot be explained by concurrent disease or other drugs or chemicals. The response to withdrawal of the study intervention (dechallenge) should be clinically plausible. The event must be pharmacologically or phenomenologically definitive., with use of a satisfactory rechallenge procedure if necessary.
2. **Probably Related** – There is evidence to suggest a causal relationship, and the influence of other factors is unlikely. The clinical event, including an abnormal laboratory test result, occurs within a reasonable time after administration of the study intervention, is unlikely to be attributed to concurrent disease or other drugs or chemicals, and follows a clinically reasonable response on withdrawal (dechallenge). Rechallenge information is not required to fulfill this definition.
3. **Potentially Related** – There is some evidence to suggest a causal relationship (e.g., the event occurred within a reasonable time after administration of the trial medication). However, other factors may have contributed to the event (e.g., the participant's clinical condition, other concomitant events). Although an AE may rate only as "possibly related" soon after discovery, it can be flagged as requiring more information and later be upgraded to "probably related" or "definitely related", as appropriate.
4. **Unlikely to be related** – A clinical event, including an abnormal laboratory test result, whose temporal relationship to study intervention administration makes a causal relationship improbable (e.g., the event did not occur within a reasonable time after administration of the study intervention) and in which other drugs or chemicals or underlying disease provides plausible explanations (e.g., the participant's clinical condition, other concomitant treatments).

5. Not Related – The AE is completely independent of study intervention administration, and/or evidence exists that the event is definitely related to another etiology. There must be an alternative, definitive etiology documented by the clinician.

8.2.3.3 EXPECTEDNESS

The medical monitor will be responsible for determining whether an AE is expected or unexpected. An AE will be considered unexpected if the nature, severity, or frequency of the event is not consistent with the risk information described in the current Investigator Brochure for IFx-Hu 2.0.

8.2.4 TIME PERIOD AND FREQUENCY FOR EVENT ASSESSMENT AND FOLLOW-UP

The occurrence of an adverse event (AE) or serious adverse event (SAE) may come to the attention of study personnel during study visits and interviews of a study participant presenting for medical care, or upon review by a study monitor.

All AEs including local and systemic reactions not meeting the criteria for SAEs will be captured on the appropriate case report form (CRF). Information to be collected includes event description, time of onset, clinician's assessment of severity, relationship to study product (assessed only by those with the training and authority to make a diagnosis), and time of resolution/stabilization of the event. All AEs occurring while on study must be documented appropriately regardless of relationship.

Any medical condition that is present at the time that the participant is screened will be considered as baseline and not reported as an AE. However, if the a pre-existing condition deteriorates at any time during the study, it will be recorded as an AE, with use of descriptors in the AE term to designate that it is a pre-existing condition (e.g., worsening of or exacerbation of)

Changes in the severity of an AE will be documented to allow an assessment of the duration of the event at each level of severity to be performed.

The investigator will record all reportable events with start dates occurring any time after informed consent is obtained until 7 (for non-serious AEs) or 30 days (for SAEs) after the last day of study participation. At each study visit, the investigator will inquire about the occurrence of AE/SAEs since the last visit. Events will be followed for outcome information until resolution or stabilization.

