1 PROTOCOL SUMMARY

1.1 SYNOPSIS

Title:	Phase 1 Trial of IFx-Hu2.0 to Evaluate Safety in Patients with Skin Cancer
Study Description:	One hundred patients will receive IFx-Hu2.0 on an outpatient basis at a single time point in a single lesion. These patients will be assessed for any immediate adverse reactions and at Week 4 (Day 28+-5 days) for any delayed adverse events.
Objectives:	
Primary Objective: To assess safety and feasibility
 
Secondary Objective: To assess post-therapeutic pathological response
 
Tertiary/Exploratory Objective: To assess anti-tumor immunity post-treatment.

Endpoints:	
Primary Endpoint: The primary endpoints of this trial will be the safety and feasibility of the treatment regimen. Safety will be reported using the most current version of the Common Terminology Criteria for Adverse Events (CTCAE). Feasibility will be defined as the ability to treat at least 85 of the approximate 100 patients enrolled without investigational product (IP) related dose-limiting toxicity (DLT).
 
Secondary Endpoints: The secondary endpoint is Pathological Response defined as a response assessment to IFx-Hu2.0 in tumor lesions excised by evaluating percent Residual Vial Tumor (%RVT), at four weeks as:
 
• pathological complete response (pCR),• major pathological response (mPR),• partial pathological response (pPR), or• pathological non-response (pNR) 
Tertiary/Exploratory Endpoints: Patient samples (plasma and/or serum) will be assayed to detect tumor antigen specific antibody generation in addition to a protein biomarker discovery assay specific to immuno-oncology therapy assessments. IHC will be performed on pre- and post-treatment tissue samples to contrast the cell sub-types across time points.

Study Population:	Adult male or female subjects with confirmed cutaneous squamous cell carcinoma, or basal cell carcinoma with lesions accessible for intralesional injection.
Phase:	Phase 1
Description of Sites/Facilities Enrolling Participants:	Approximately 5 NCI-designated cancer centers, academic medical centers, clinics, and doctor's offices within the United States, qualified to perform clinical studies under GCP.
Description of Study Intervention:	Plasmid DNA encoding a Streptococcal antigen in a cationic polymer-based solution in doses of 100 µg delivered intralesionally at a single time point "Week 0".
Study Duration:	12 Months
Participant Duration:	Up to six weeks

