7.2 PARTICIPANT DISCONTINUATION/WITHDRAWAL FROM THE STUDY

Participants are free to withdraw from participation in the study at any time upon request.

An investigator may discontinue or withdraw a participant from the study for the following reasons:

1. Pregnancy

2. Significant study intervention non-compliance
3. If any clinical adverse event (AE), laboratory abnormality, or other medical condition or situation occurs such that continued participation in the study would not be in the best interest of the participant
4. Disease progression
5. If the participant meets an exclusion criterion or fails to meet an inclusion criteria (either newly developed or not previously recognized) that precludes further study participation

The reason for participant discontinuation or withdrawal from the study will be recorded on the case report form (CRF). Subjects who sign the informed consent form but do not receive the study intervention may be replaced. Subjects who sign the informed consent form, and receive the study intervention, and subsequently withdraw, or are withdrawn or discontinued from the study will be replaced.

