9.2 SAMPLE SIZE DETERMINATION

The intent of this study is to enroll approximately 100 evaluable patients to assess the safety of IFx-Hu2.0 as a monotherapy. A sample size of 100 has the following precision for estimation of DLT rates ranging from 0.1 to 0.5. A DLT is defined as an adverse event equal to or greater than grade 3, at least possibly related to the investigational agent, occurring within a 4-week period following IP administration, and deemed as having unacceptable toxicity by the principal investigator and/or medical monitor. Precision is measured by 1-sided 95% upper confidence limit on the estimated DLT rate via exact binomial distribution. For example, if no DLT is observed in patients on IFX-Hu 2.0, then the true underlying DLT rate is lower than 0.099 with 95% confidence.

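### For a treated participant who leaves before Day 21, recording of new non-serious adverse events closes before the 4-week DLT window ends

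*Protocol*

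**What the plan says.** **Recording window.** Protocol section 8.2.4 sets the limit by event start date, counted from departure: "until 7 (for non-serious AEs) or 30 days (for SAEs) after the last day of study participation".

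**DLT window.** Protocol section 9.2 counts from the dose: "occurring within a 4-week period following IP administration". SAP sections 2.2.1, 2.3 and 3.7 use the same 4 weeks.

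**What a DLT is.** Section 9.2 begins: "A DLT is defined as an adverse event equal to or greater than grade 3, at least possibly related to the investigational agent". It then adds that the principal investigator or medical monitor, or both, must judge the toxicity unacceptable. SAP section 2.3 repeats that condition; SAP sections 2.2.1 and 3.7 leave it out. None of these definitions requires the event to be serious. Section 8.2.2 defines seriousness by outcome, not CTCAE grade: an event is serious if "in the view of either the investigator or sponsor, it results in any of the following outcomes".

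**When events are looked for.** The synopsis plans assessment "at Week 4 (Day 28+-5 days) for any delayed adverse events". Section 8.1 documents events from Day 0 and "as well as at the follow-up visit whether that be end of study as planned or early termination". The Schedule of Activities has unscheduled and early termination visits, but no contact after early termination.

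**Who is counted.** SAP section 3.2.1 reports the DLT rate on the safety analysis set, which is everyone dosed, and SAP section 3.4 rules out imputation. Protocol section 7.2 replaces dosed participants who leave. The stopping boundary in section 9.4.2 uses only patients whose follow-up is complete.

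**The concern.** The two windows start from different days. The event of interest is timed from dosing, while the duty to record it is timed from departure. They agree for anyone who attends the final visit, but not for someone who leaves early. A new grade 3 local reaction or laboratory abnormality in week 3 or 4 could meet the DLT definition without being serious, and no rule would require the site to record it.

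The DLT is the event behind the reported DLT rate and the feasibility criterion. That criterion is a fixed count, printed as 85 in the synopsis and SAP section 2.2.1 and as 80 in Protocol sections 3 and 9.4.1. A leaver with an unrecorded DLT is counted as having none, so the error runs in the favourable direction. No analysis can later restore an event that was never recorded.

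**Working it through.** The plan gives no figure for this gap, so there is none to reproduce. The check compares the two windows, then looks for any other provision that closes the gap.

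**1. Inputs.** Dose on Day 0; DLT window to Day 28 (section 9.2); recording to d + 7 for non-serious events and d + 30 for serious events, where d is the last day of participation (section 8.2.4); final visit on Day 23 to Day 33 (synopsis).

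**2. Days outside the rule.** Uncovered days = max(0, 28 − (d + 7)) = max(0, 21 − d).

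| Last day d | Non-serious recorded to | Uncovered days of 28 |
|---|---|---|
| 0 | Day 7 | 21 (75%) |
| 3 | Day 10 | 18 (64%) |
| 7 | Day 14 | 14 (50%) |
| 10 | Day 17 | 11 (39%) |
| 14 | Day 21 | 7 (25%) |
| 20 | Day 27 | 1 (4%) |
| 21 or later | Day 28 or later | 0 |

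**3. What is covered.** The earliest on-time final visit is Day 23, which gives recording to Day 30, so completers have no gap. Serious events are recorded to at least Day 0 + 30 = Day 30, so serious DLTs have no gap. The limit applies to start dates. Under section 8.2.4 an event that has already begun is followed to resolution or stabilization, and section 8.2.1 records it at its worst grade. A grade 2 reaction present at departure that later reaches grade 3 is therefore inside the rule. What remains is the new-onset, non-serious DLT.

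**4. Other provisions.** Sections 7.1 and 8.1 follow toxicity that is already under way; they do not look for new events. Unscheduled visits fall between baseline and the final visit and are not a contact for someone who has left. The 28-day treatment-emergent definition in SAP section 3.2.1 classifies events already in the database; it does not collect them. None of these closes the gap.

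**5. Where leavers enter the analysis.** They stay in the safety analysis set with nothing imputed, so the reported DLT rate is exposed, as is any feasibility count based on treated participants. In the stopping rule they need not appear, because n counts patients with complete follow-up.

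**6. Size, under assumptions.** The documents give no dropout rate, leaving pattern or onset distribution. Assume a fraction f leaves on Day 7, onset is uniform over 28 days and independent of leaving, and all DLTs are non-serious. The unrecorded share is f × 14/28.

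- f = 5%: 2.5%; a true rate of 0.15 is recorded as 0.146.
- f = 10%: 5%; 0.15 is recorded as 0.1425.
- f = 20%: 10%; 0.15 is recorded as 0.135.

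If departures were instead uniform over Days 0 to 28, the average uncovered share per leaver would be (21²/2)/28² = 220.5/784 = 28.1%. Ten leavers at a 15% risk would then give 10 × 0.15 × 0.281 = 0.42 unrecorded DLTs.

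**7. Outer bounds.** Suppose 100 are treated and no DLT is recorded. The exact one-sided 95% upper limit is 1 − 0.05^(1/100) = 0.030. With 5 incompletely observed leavers it is 0.031 on the 95 observed, and 0.102 if all 5 had an unrecorded DLT. With 10 leavers the two figures are 0.033 and 0.164. The second figure of each pair is an extreme, not an expectation.

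**The case against.** The strongest reply is that little is left once the other provisions are read together. Serious events are covered, section 8.2.2 lets important medical events be classed as serious on medical judgement, and events begun before recording closes are followed. Sections 9.2 and SAP 2.3 narrow DLTs further by requiring a judgement of unacceptable toxicity. The study has three visits over about six weeks. Section 7.3 already asks for calls and rescheduling after a missed visit. The earlier monotherapy trial reported no grade 3 to 5 treatment-related event in six evaluable patients. All of this stands, and it limits the size. It does not bring Day 28 inside the recording rule for someone who leaves on Day 10.

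Two wording points also matter. The last day of study participation is not defined; read as the planned final visit, it would close the gap. However, sections 7.2 and 7.3 treat leavers as withdrawn from the study, so the natural reading is the actual last day. In the other direction, sections 7.1 and 8.1 let follow-up of ongoing toxicity end on removal from the trial, so the cover for events already begun rests on section 8.2.4, which has no such exception.

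A reader might infer more than the documents support:

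- **That the participants most likely to be developing a DLT are those least observed.** A toxicity that prompts departure has already started and is recordable. Applying a high risk such as 50% to leavers, to give 10 × 0.50 × 0.281 = 1.4 unrecorded events, treats onset as independent of a toxicity that has already begun.
- **That any shift in a laboratory value or start of a new medicine ends observation.** Section 7.2 lists "If the participant meets an exclusion criterion or fails to meet an inclusion criteria (either newly developed or not previously recognized", but confines this to cases that rule out continuing, and the investigator may, rather than must, withdraw the participant.
- **That section 8.1 allows documentation at the last visit alone.** It does not say so, and section 8.2.4 also accepts events found when a participant presents for medical care or on monitor review.
- **That the stopping boundary is compromised.** It counts patients with complete follow-up, and treated leavers are replaced.

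**Conclusion.** The concern holds in a narrow form. For a treated participant who leaves on Day d below 21, new-onset non-serious events in the last 21 − d days of the DLT window lie outside the recording rule, and no provision requires a Day 28 contact. That part is certain from the text, given the natural reading of the last day of participation.

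The consequence is a possible favourable bias in the all-treated DLT rate and in any feasibility count based on treated participants. Its size cannot be derived from the documents and is probably modest: 2.5% to 10% of non-serious DLTs under the Day 7 scenarios, which is about 0.4 to 1.5 events per 100 treated at a true rate of 0.15 (100 × 0.15 × 0.025 to 100 × 0.15 × 0.10). A difference of that size changes the feasibility conclusion only if the count lies at the threshold. It is a cheap improvement worth making, not a flaw that undermines the trial.

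**What to change.** - **Section 8.2.4:** record non-serious adverse events until the later of Day 28 after dosing and 7 days after the last day of participation. Leave the limit for serious events unchanged, and define the last day of participation.
- **Section 7.2:** state that withdrawal after dosing, for any listed reason, does not end adverse event recording through Day 28 unless the participant withdraws consent for contact. This leaves the decision to withdraw untouched.
- **Schedule of Activities:** add a Day 28 telephone or chart check for early leavers, asking about any new event of grade 3 or higher.

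With these changes the recording rule leaves no uncovered days for any leaving day. The cost is protocol wording and one brief contact or chart check per early leaver. The change cannot guarantee data after loss to follow-up or withdrawal of consent, so the SAP should also report, beside the DLT rate, how many treated participants had less than 28 days of recording.

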8.2.5 ADVERSE EVENT REPORTING

Adverse events will be documented. The principal investigator at the site is responsible for notifying the sponsor of any adverse event as soon as possible. The medical monitor will review all adverse event reports and ensure that participants are receiving appropriate clinical care and identify any potential safety concerns. The medical monitor will assess the information provided to determine the relatedness of the event to the study intervention as well as propose any changes to the protocol and/or consent form based on the event. All adverse events will be documented and reported to the FDA in the annual report. Adverse events that meet the requirements for reporting to the IRB will be reported within the guidelines required by the IRB of record, along with necessary supporting information and revised trial documentation, as necessary.

